#### **2.3.2.7 EQ-5D-5L at 24 Weeks**

The European Quality of Life-5 Dimensions-5 Levels (EQ-5D-5L) index utility score using the U.K. value set and visual analogue scale (VAS) will be evaluated at 24 weeks in the study. These two endpoints will be analyzed as described in the efficacy analysis section but will not be part of the hierarchical testing procedure.

#### **2.3.3 Exploratory Efficacy Endpoints**

The exploratory efficacy endpoints are as follows:

- Patient satisfaction with treatment [REDACTED]
- Treatment preference for emicizumab prophylaxis versus FVIII prophylaxis or episodic therapy according to the preference survey
- Number of days away from school/work
- Number of days hospitalized
- [REDACTED]

#### **2.3.4 Pharmacokinetic Endpoints**

The pharmacokinetic (PK) endpoint for this study is the exposure (trough plasma concentration) to emicizumab at the following timepoints:

- Every week during Weeks 1–4 on emicizumab
- Every 2 weeks during weeks 5–8 on emicizumab
- Every 4 weeks during weeks 9–24 on emicizumab
- Every 8 weeks during weeks 25–48 on emicizumab

- Every 12 weeks thereafter while on emicizumab until the end of the study

### **2.3.5 Safety Endpoints**

Safety parameters to be measured include exposure, adverse events (including serious adverse events, adverse events of special interest, adverse events leading to drug discontinuation, and deaths), clinical laboratory results (hematology, chemistry, anti-FVIII and anti-emicizumab antibodies), vital signs, ECG, and concomitant medication use.

### **2.3.6 Exploratory Biomarker Endpoints**

Exploratory biomarker endpoints include

- Pharmacodynamic (PD) biomarkers of emicizumab, including but not limited to aPTT, thrombin generation, and FVIII activity

- 

## **2.4 DETERMINATION OF SAMPLE SIZE**

The sample size for this study is based on clinical rather than statistical considerations, taking into account the limited number of patients with hemophilia A without inhibitors available for participation in clinical studies and in an effort to collect sufficient data to assess the safety and efficacy of emicizumab.

The sample size calculation is based on the evaluation of the primary efficacy endpoint, defined as the number of bleeds over time (i.e., bleed rate) with emicizumab (treatment group,  $\lambda_t$ ) versus no prophylaxis (control group,  $\lambda_c$ ), which are said to follow a negative binomial (NB) distribution. With consideration of enrollment feasibility, a sample size of 75 patients, assuming an allocation ratio of 2:2:1 (30 patients in each randomized treatment group and 15 patients in control group), will achieve a power of more than 90% assuming a mean ABR of 4 and 14 bleeds (with variances = mean  $\times$  10) for the emicizumab treatment and control arms respectively, representing an expected 71% reduction in the ABR compared to the control arm. Initial sample size calculations were performed with East®, Version 6 (Cytel, Cambridge, MA), assuming the patients from each treatment group are followed up to 0.5 units of time (i.e., 24 weeks).

However, the above approach to sample size calculation assumes similar follow-up for each patient. Because this is unlikely to be seen in the study, power was also estimated by simulation to account for different follow-up times among patients. Conducting simulations on the basis of an NB regression model including an offset variable to account for variable follow-up times, with all other assumptions remaining the same as previously described, the sample size is projected to have greater than 90% power at the 2-sided 0.05 level of significance.

The analysis will include all enrolled patients regardless of their length of follow-up. Therefore, to ensure the analysis is based on sufficient follow-up data and with 2:2:1 treatment to control randomization, approximately 34 patients in each randomized

[figure not shown]

emicizumab treatment arm (68 in total) and 17 patients in the control arm (approximately 85 patients in total) will be enrolled.

With a minimum of 40 and a maximum of 60 patients enrolled in the open-label prophylactic emicizumab arm, and assuming a mean ABR of 4 and variance of  $4 \times 10$ , this number is considered sufficiently powered to evaluate the efficacy endpoint in this cohort; the treatment will be considered to provide adequate control if the upper limit of the one sided 97.5% CI around the mean ABR is less than or equal to 6.

The primary safety consideration in determining the sample size was the ability to sufficiently evaluate the safety profile of emicizumab as assessed by adverse events. Under the assumption that the occurrence of an adverse event can be adequately modeled using the binomial distribution, the planned sample size of 108–128 patients in the emicizumab treatment groups allows observation of adverse events having a true incidence rate of 1% with a probability of 0.66–0.72.

No sample size re-assessment of the initially specified sample size will be performed.

## **2.5 ANALYSIS TIMING**

The primary efficacy analysis to assess the effect of emicizumab on bleed rate reduction will be performed at the earliest timepoint when all randomized patients (Arms A, B, and C) and a minimum of 40 patients from Arm D have either completed 24 weeks of study treatment or discontinued from the study.

The final analysis will occur at the end of the study, as defined in the protocol. No interim analysis is planned for the study.

## **3. STUDY CONDUCT**

### **3.1 RANDOMIZATION ISSUES**

Patients who received episodic treatment with FVIII prior to study entry will be randomized in a 2:2:1 ratio to receive either emicizumab prophylaxis at 3 mg/kg/wk subcutaneously for 4 weeks, followed by 1.5 mg/kg/wk (Arm A) or 3 mg/kg/2wks (Arm B) subcutaneously, or to the control arm (no prophylaxis; Arm C). The time between screening and enrollment of eligible patients should be  $\leq 6$  weeks; otherwise, patients must be re-screened to determine if they continue to meet the inclusion and exclusion criteria. A central randomization procedure will be used for all patients who fulfill the

entry criteria at screening. A block based randomization method will be used, stratified by the number of bleeds in the last 24 weeks ( $<9$  or  $\geq 9$ ). The proposed randomization method is designed to balance treatment group assignment within the prognostic stratification factor.

Patients on FVIII prophylaxis prior to study entry will be enrolled in a separate therapeutic arm to receive emicizumab prophylaxis (Arm D).

### **3.2 DATA MONITORING**

An independent Data Monitoring Committee (iDMC) has been assembled to review the safety data collected during the study. The iDMC members consist of, at a minimum, independent hemostasis/thrombosis experts and a statistician, none of whom are otherwise involved in the conduct of study. All analyses for review by the iDMC are prepared by an independent Data Coordinating Committee (iDCC) that is independent of the Sponsor.

An iDCC performs unblinded analyses and provides tables and listings to support the iDMC reviews of safety data. The safety data include demographic data, adverse events, serious adverse events, and laboratory abnormalities (coagulation, hematology, and chemistry). Further information will be given by the iDCC to the iDMC on request.

Following each meeting, the iDMC will recommend to the Sponsor whether the study should continue according to the protocol or may suggest changes to the protocol based on the outcome of the data review. In exceptional cases, the iDMC may recommend stopping the study or closing a treatment arm for safety reasons. The iDMC will monitor the incidence of the anticipated adverse events, as well as the overall safety of patients, during the study.

The first safety review was conducted after 25 episodic patients (i.e., randomized to Arms A, B, or C) had been in the study for at least 2 months, and the iDMC recommended to continue. Thereafter, the iDMC will meet at a frequency determined by the iDMC and the Sponsor according to the emerging safety profile.

Further details are provided in a separate iDMC Charter.

## **4. STATISTICAL METHODS**

### **4.1 OUTPUT LAYOUTS**

The key output layouts are designed to address the study objectives in a flexible manner and provide an overall view of the efficacy and safety of emicizumab. In particular, patients in Arm C are allowed to switch to receive emicizumab after the first 24 weeks in the study, yielding two “study periods” (i.e., when they receive no prophylaxis for the first 24 weeks [no prophylaxis period, designated Arm Ccontrol] and emicizumab prophylaxis thereafter [emicizumab period, designated Arm Cemi]). These two periods are analyzed

separately, and either period can be displayed on outputs together with the other treatment arms.

The four key output layouts are:

- **Randomized patients:** comparison of either emicizumab 1.5 mg/kg/wk (Arm A) versus no prophylaxis (control arm [Arm Ccontrol] prior to switch to emicizumab) or emicizumab 3 mg/kg/2wks (Arm B) versus no prophylaxis (Arm Ccontrol), within a single output produced for all comparisons involving arms A, B, and C prior to switch (Arm A versus Arm Ccontrol and Arm B versus Arm Ccontrol); these outputs form the core set of the efficacy comparisons and will be supported by a corresponding safety analysis
- **All patients:** these outputs will be used to describe the baseline characteristics and study conduct
- **All emicizumab patients:** these outputs will provide an overall view of all data collected under emicizumab prophylaxis (including control arm patients after switch [Arm Cemi]) and will include analyses of safety and descriptive efficacy
- **Intra-patient comparisons:** Arm D is displayed separately with its own historical control (for Arms A and B, the patients are combined; see Section 4.5.2.6); for evaluations of the secondary endpoint with intra-patient comparisons, only patients who participated in the NIS BH29768 are included

Of note, patients may be allowed to up-titrate their emicizumab dose as described in Section 2. The data under the new, higher dose are analyzed and reported separately. Additional summaries will be produced for key safety and exposure on all data (i.e., data before and after up-titration). Note, with longer follow-up or in case up-titration occurs more frequently than expected, outputs on all data may form the core analysis and additional summaries will be produced by dose.

## 4.2 ANALYSIS POPULATIONS

### 4.2.1 Randomized Population (ITT)

The randomized population (intent-to-treat [ITT]) is defined as all randomized patients. The ITT population will be the primary analysis population for efficacy. Patients are analyzed according to their randomized treatment arm. Note that this population only includes patients in Arms A, B, and C.

### 4.2.2 All Patients

The All Patients population includes all patients in their originally assigned treatment arms (including patients in Arm D previously treated with prophylactic FVIII), according to the interactive voice or Web Response System (IxRS).

#### **4.2.3 All Emicizumab Patients**

The All Emicizumab Patients population is the same as the All Patients population for Arms A, B, and D. For Arm C, only patients who switch to receive emicizumab are included.

#### **4.2.4 Pharmacokinetic-Evaluable Population**

The PK-Evaluable population includes all patients who have received at least one dose of emicizumab and have at least one post-baseline emicizumab concentration result.

#### **4.2.5 Safety Population**

Two safety analysis populations are defined below:

- Safety Population 1 (SAF1) includes all patients in Arms A, B, and D who received at least one dose of emicizumab and patients in Arm C who started the study period, defined as having a Week 1 visit. For safety analysis of randomized patients, a subset of the SAF1 population (SAF1ND) will be used, which excludes patients in Arm D.
- Safety Population 2 (SAF2) is exactly the same as SAF1 for patients in Arms A, B, and D. For patients in Arm C, SAF2 includes all patients who switched to emicizumab and received at least one dose of emicizumab.

#### **4.2.6 Up-titrated Population**

The Up-Titrated population (UPT) includes patients whose emicizumab dose was up-titrated to 3 mg/kg/wk.

#### **4.2.7 Non-Interventional Study (NIS) Population**

The NIS population includes all patients who participated in NIS BH29768 prior enrollment to this study. The NIS population includes two subpopulations:

- The NISE population consisting in all the above NIS population previously treated with episodic FVIII
- The NISP population consisting in all the above NIS population previously treated with prophylactic FVIII

#### **4.2.8**

[Redacted text block]

[Redacted text block]

[Redacted text block]

### **4.3 ANALYSIS OF STUDY CONDUCT**

Flow of patients through the study will be displayed in a “CONSORT” diagram. A clear account of all patients who entered the study, who were enrolled and randomized, and who entered and completed each phase of the study will be displayed. In addition, reasons for premature discontinuations from study treatment and reasons for withdrawing from the study (e.g., during follow-up) will be described.

Major protocol deviations will be summarized.

Observation time and duration of follow-up, as well as adherence to planned scheduled assessments and compliance with data entry into the electronic handheld device will also be evaluated.

### **4.4 ANALYSIS OF TREATMENT GROUP COMPARABILITY**

Comparisons between the treatment arms of demographic data (e.g. age, sex, race/ethnicity, weight, and height) and baseline disease characteristics (e.g., number of bleeds in the past 24 weeks, previous hemophilia treatments, and number of target joints) will be conducted to establish if any observed differences between the treatment arms are not due to imbalances in patient characteristics at baseline. Only descriptive analyses are planned, and no formal statistical tests will be applied.

### **4.5 EFFICACY ANALYSIS**

The primary and secondary efficacy analyses will be based on the All Patients population (see section [4.2.2](#)).

#### **4.5.1 Primary Efficacy Endpoint**

The primary efficacy objective is to evaluate the clinical effect of prophylactic emicizumab compared with no prophylaxis on the number of bleeds over time. The definition of a bleed is described in Section [2.3.1](#). The primary endpoint is based on treated bleeds.

The comparison of the number of bleeds over time between the randomized treatment arms will be performed using an NB regression model, which accounts for different follow-up times, with the patient’s number of bleeds as a function of randomization and the time that each patient stays in the study (the length of the efficacy period) included as an offset in the model. The model also includes the number of bleeds ( $<9$  or  $\geq 9$  according to the eCRF data) in the last 24 weeks prior to study entry as a stratification factor. This analytic model estimates the rate ratio,  $\lambda_t/\lambda_c$ , which quantifies the risk of bleeding associated with prophylactic emicizumab ( $\lambda_t$ ) in comparison to no prophylaxis ( $\lambda_c$ ). Statistical significance is controlled at the 2-sided, 0.05 alpha ( $\alpha$ ) level.

Of note, hierarchical testing is used to account for multiple testing and the first test to be included in the hierarchy is the emicizumab 1.5 mg/kg/wk maintenance dose versus

control. The second test will be 3 mg/kg/2wks maintenance dose versus control. A global approach using a model statement (within GENMOD) with a 3-level categorical effect for treatment (“1.5 mg/kg/wk,” “3 mg/kg/2wks,” or “no prophylaxis”) and an appropriate contrast statement will allow both tests to be performed via the following hypothesis

$H_0$  (null hypothesis): Rate Ratio = 1 versus  $H_1$  (alternative hypothesis): Rate Ratio  $\neq$  1.

Statistical significance at the prespecified  $\alpha$  level will be based on a Wald testing procedure. Bleed rates for prophylactic emicizumab and no prophylaxis and the rate ratio will be presented and include 95% CIs.

The number of bleeds can also be annualized for each patient using the following formula:

$$ABR = (\text{Number of bleeds} / \text{Total number of days during the efficacy period}) \times 365.25.$$

Both the model-based method (estimated ABR from the NB model) and the method using the above formula (calculated ABR) will be used to describe the study results.

If the NB model converges, the Van Elteren test to compare the mean ABR between the randomized arms will be provided as a sensitivity analysis. However, if the convergence of the NB model is not achieved or is questionable or no bleeds at all were observed in one of the treatment arms, the primary efficacy analysis will be based on the Van Elteren test of ABR, according to the above formula.

Of note, the Van Elteren test will be applied separately for the Arm A versus Arm  $C_{\text{control}}$  (using only patients randomized to Arms A and  $C_{\text{control}}$ ) and for the Arm B versus Arm  $C_{\text{control}}$  comparisons.

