3.3 RATIONALE FOR STUDY DESIGN

The Sponsor proposes a randomized, multicenter, open-label, Phase III clinical study that will enroll patients aged 12 years or older with severe hemophilia A (intrinsic FVIII level < 1%) without inhibitors against FVIII. In the randomized arms of the study, patients who received episodic treatment with FVIII prior to enrollment will be randomized to receive one of the following regimens:

- Emicizumab prophylaxis at 3 mg/kg/wk for 4 weeks, followed by 1.5 mg/kg/wk subcutaneously (Arm A),
- Emicizumab prophylaxis at 3 mg/kg/wk for 4 weeks, followed by 3 mg/kg/2wks subcutaneously (Arm B), OR
- No prophylaxis control arm (Arm C).

This prospective, randomized design allows uniform collection of bleed data, medication use and patient-reported outcomes through the utilization of patient-validated measurement tools in all groups, enabling analysis of the effect of emicizumab versus episodic FVIII therapy on these important measures. Reporting of bleeds by patients to their providers (e.g., doctors, nurses) is not standardized and can be incomplete in routine clinical care. In addition, the recording of bleeds by providers in medical records may be inconsistent. Therefore, testing the primary endpoint using a prospective randomized design is superior to comparison to historical control in patients who were not on prophylaxis prior to enrollment.

Given the proven efficacy of FVIII prophylaxis, it can be expected that standard-of-care may evolve towards more widespread treatment of patients with prophylaxis regimens. However, for myriad of reasons currently only about half the patients in developed countries are managed with routine prophylaxis, making the episodic approach a commonly used standard care (Richards et al. 2007; Gringeri et al. 2012; Zappa et al. 2012; Jackson et al. 2014, 2015; Oldenburg and Brackmann 2014; Oldenburg 2015). Thus, for the primary efficacy endpoint, patients on episodic FVIII will be compared with patients treated with prophylactic emicizumab. Limiting the randomized portion of the study and primary efficacy analysis to patients who previously received episodic FVIII will reduce heterogeneity in the study population, which is appropriate since the bleed rates for patients receiving therapy on an episodic versus prophylactic basis are significantly different (Valentino et al. 2012; Manco-Johnson et al. 2013; Powell et al. 2013; Antunes et al. 2014;

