3.3.3 Rationale for Control Group

The control group for the primary efficacy endpoint will be a concurrent, no prophylaxis “usual care” arm, to which patients who were on episodic FVIII prior to study entry will be randomized (2:2:1 prophylactic emicizumab 1.5 mg/kg/wk:prophylactic emicizumab 3 mg/kg/2wks:no prophylaxis), which will enable an inter-patient comparison of the

treatment and control groups. All patients, whether assigned to receive prophylactic emicizumab or no prophylaxis, will continue to receive FVIII on an episodic basis for the treatment of breakthrough bleeds during the study. Specific doses of FVIII will not be mandated in the study, but investigators should review with patients the dose to be used to treat breakthrough bleeds. Breakthrough bleeds should be treated with the lowest FVIII dose expected to achieve hemostasis, which may be lower than the patients' prior FVIII dose.

A second comparison will be an individual patient's bleed rate calculated over the 24 weeks prior to study entry, from the medical record and/or Study BH29768. This will enable intra-patient analyses of bleed rates to be performed.

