4.1.1 Inclusion Criteria

Patients must meet the following criteria for study entry:

- Signed Informed Consent Form by the patient or a legal guardian
- Able to comply with the study protocol, in the investigator's judgment

- Willingness and ability to comply with scheduled visits, treatment plans, laboratory tests, and other study procedures, including the completion of patient-reported outcome questionnaires and bleed and medication diary through the use of an electronic device
- Aged 12 years or older at the time of informed consent
- Body weight ≥ 40 kg at the time of screening
- Diagnosis of severe congenital hemophilia A (intrinsic FVIII level $< 1\%$)
- A negative test for inhibitor (i.e., < 0.6 BU) within 8 weeks of enrollment
- No documented inhibitor (i.e., < 0.6 BU), FVIII half-life < 6 hours, or FVIII recovery $< 66\%$ in the last 5 years
- Patients who completed successful immune tolerance induction (ITI) at least 5 years before screening are eligible, provided they have had no evidence of inhibitor recurrence (permanent or temporary) as may be indicated by detection of an inhibitor, FVIII half-life < 6 hours, or FVIII recovery $< 66\%$ since completing ITI (Antun et al. 2015).
- Documentation of the details of prophylactic or episodic FVIII treatment and of number of bleeding episodes for at least the last 24 weeks
- For patients on no prophylaxis (episodic treatment) pre-study, ≥ 5 bleeds in the last 24 weeks prior to study entry
- Patients who were on FVIII prophylaxis for at least the last 24 weeks, can be enrolled regardless of the number of bleeds during this period. Eligibility will be based on investigator's attestation of adequate prophylaxis regimen.
- At least 40 patients who were on FVIII prophylaxis pre-enrollment will have been enrolled for a minimum of 24 weeks in Study BH29768 (non-interventional)
- Adequate hematologic function, defined as platelet count $\geq 100,000/\mu\text{L}$ and hemoglobin ≥ 8 g/dL (4.97 mmol/L) at the time of screening
- Adequate hepatic function, defined as total bilirubin $\leq 1.5 \times$ the upper limit of normal (ULN) (excluding Gilbert's syndrome) and both AST and ALT $\leq 3 \times$ ULN at the time of screening; no clinical signs or known laboratory/radiographic evidence consistent with cirrhosis
- Adequate renal function, defined as serum creatinine $\leq 2.5 \times$ ULN and creatinine clearance by Cockcroft-Gault formula ≥ 30 mL/min

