4.5.2 Medical History and Demographic Data

Medical history includes clinically significant diseases, procedures, use of alcohol and drugs of abuse within the past year, and medication allergies. In particular, sites should record whether the patient has any history of FVIII inhibitor, anaphylaxis or known thrombophilia. It should also include all medication taken in the 4 weeks prior to screening (including prescription, over-the-counter, and herbal/homeopathic remedies and therapies) or in the 24 weeks prior to screening for medications intended to treat osteopenia or osteoporosis. If imaging tests of bone health (e.g., densitometry, dual energy X-ray absorptiometry [DEXA]) were performed in the year prior to screening, the results should be recorded. Finally, number of bleeds during the 24 weeks prior to study enrollment should be documented, as well as the number of school/work days missed and number of days hospitalized during the 24 weeks prior to study entry.

Demographic data will include age, sex, and self-reported race and ethnicity.

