6.5.1 Primary Efficacy Endpoint

The primary efficacy objective is to evaluate the clinical effect of prophylactic emicizumab compared with no prophylaxis on the number of bleeds over time. The definition of a bleed is described in Section 4.5.8. The primary endpoint is based on treated bleeds.

The primary efficacy analysis will be conducted after all randomized patients (and a minimum of 40 patients previously treated with prophylactic FVIII) have completed

24 weeks in the study or the last randomized patient yet to complete 24 weeks in the study discontinues study participation, whichever occurs first, and using an intent-to-treat principle. The comparison of the number of bleeds over time between the randomized treatment arms will be performed using an NB regression model, which accounts for different follow-up times, with the patient's number of bleeds as a function of randomization and the time that each patient stays in the study included as an offset in the model. The model also includes the number of bleeds (< 9 or ≥ 9) in the last 24 weeks prior to study entry as a stratification factor in the randomization. This analytic model estimates the rate ratio, λ_t/λ_c , which quantifies the risk of bleeding associated with prophylactic emicizumab (λ_t) in comparison to no prophylaxis (λ_c). Statistical significance is controlled at the 2-sided, 0.05 alpha (α) level. Of note, hierarchical testing is used to account for multiple testing and the first test to be included in the hierarchy is the emicizumab 1.5 mg/kg/wk maintenance dose versus control. The second test will be 3 mg/kg/2wks maintenance dose versus control. The description below covers both hypotheses to be tested:

H_0 (null hypothesis): Rate Ratio = 1 versus H_1 (alternative hypothesis): Rate Ratio $\neq 1$.

The treatment effect therein is based on a contrast statement in the model with use of the SAS GENMOD procedure. Statistical significance at the prespecified alpha level will be based on a Wald testing procedure. Bleed rates for prophylactic emicizumab and no prophylaxis and the rate ratio will be presented and include 95% confidence intervals.

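### The primary negative binomial model uses prior bleeding only as <9 versus ≥9; adding the recorded 24-week count is a cheap efficiency gain of uncertain size, not a correction of an error

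*SAP*

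**What the plan says.** SAP 4.5.1 fits an NB regression with a three-level treatment effect, follow-up time as offset, and prior bleeding as a two-class term (<9 or ≥9) "according to the eCRF data) in the last 24 weeks prior to study entry as a stratification factor". Protocol 6.5.1 has the same term, described as bleeds "in the last 24 weeks prior to study entry as a stratification factor in the randomization". On the test level, the SAP states: "Statistical significance is controlled at the 2-sided, 0.05 alpha".

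The underlying number is available. Protocol 4.5.2 says that the "number of bleeds during the 24 weeks prior to study enrollment should be documented", and eligibility for the randomised arms requires "≥ 5 bleeds in the last 24 weeks prior to study entry" (Protocol 4.1.1). SAP 4.4 lists "number of bleeds in the past 24 weeks, previous hemophilia treatments, and number of target joints" among the baseline characteristics, for descriptive comparison only. None of the sensitivity analyses in SAP 4.5.4 uses the count.

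SAP 4.5.2.1–4.5.2.3 apply the primary model to all bleeds, treated spontaneous bleeds and treated joint bleeds. With two comparisons each, that makes six further tests in the hierarchy of SAP 4.5.2.

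**The concern.** The plan treats bleeding history as prognostic. It is the only stratification factor, it sets the entry threshold, and each patient's own history is a planned second comparator (Protocol 3.3.3). Yet the primary model keeps one binary piece of it. Eligible patients in the lower class have 5 to 8 prior bleeds; the upper class is open-ended, so whatever prognostic gradient lies above 9 is left in the residual spread.

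That spread is what limits precision here. The sample-size section assumes a variance ten times the mean, with 17 controls. Variance removed by a better baseline covariate would narrow the confidence intervals. It would also raise the chance that both primary comparisons succeed, which the hierarchy requires before any secondary endpoint is tested.

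**Working it through.** **Step 1. Reproduce the plan's power (SAP 2.4).** Inputs: ABR 4 versus 14, variance = 10 × mean, 30 versus 15 patients, 0.5 years, two-sided 0.05. On the annual scale, mean + k·mean² = 10·mean gives k = 9/mean, so k = 9/4 = 2.25 on emicizumab and 9/14 = 0.643 on control. For the Wald test on the log rate ratio:

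SE² = (1/(t·μ₁) + k₁)/n₁ + (1/(t·μ₀) + k₀)/n₀

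- 30 versus 15: (0.5 + 2.25)/30 + (0.143 + 0.643)/15 = 0.0917 + 0.0524 = 0.1440; SE 0.3795. With ln(14/4) = 1.2528, power = Φ(1.2528/0.3795 − 1.96) = 91.0%, matching the stated figure.
- 34 versus 17 (enrolled): 0.0809 + 0.0462 = 0.1271; SE 0.3565; power 94.0%.

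**Step 2. Probability that both primary tests pass.** The two log rate ratios share the control arm, so their correlation is 0.0462/0.1271 = 0.36. With bivariate normal statistics, both pass with probability 84.1% at 30/30/15 and 89.1% at 34/34/17. This assumes 0.5 years in every arm; longer emicizumab follow-up would raise it.

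**Step 3. Effect of adding log prior count to the factor.** The documents give neither the distribution of prior counts nor their relation to on-study bleeding, so both are assumptions. The simulation used:

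- a 24-week Poisson-lognormal prior count truncated at ≥5, with prior rate median 20 per year (alternative 14) and log-SD 0.7;
- an on-study log rate with correlation ρ to the prior log rate;
- control calibrated to ABR 14 and k of about 0.64, and emicizumab at 4/14 of the control rate, with and without extra heterogeneity toward k = 2.25;
- arms of 34/34/17 and 1,500 replicates per setting.

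The table gives the empirical variance of the log rate ratio (Arm A versus C) for factor plus log count, divided by that for the factor alone.

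| ρ | Variance ratio | Change |
|---|---|---|
| 0 | 1.01–1.02 | 1–2% inflation |
| 0.3 | 0.99 | about 1% reduction |
| 0.5 | 0.95–0.96 | about 5% reduction |
| 0.7 | 0.87–0.93 | about 7–13% reduction |
| 0.9 | 0.70–0.77 | over 20% reduction |

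The ranges cover the two heterogeneity settings and, at 0.5 and 0.7, both prior-rate medians. The inflation at ρ = 0 agrees with a simple count: one extra coefficient out of 85 − 4 = 81 residual degrees of freedom is about 1.2%.

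**Step 4. What this means for success.** Applying these ratios to the 34/34/17 variance in Step 1 is illustrative, because that formula carries no covariates.

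| Variance ratio | Power, one comparison | Both primary tests pass |
|---|---|---|
| 1.02 | 93.6% | 88.4% |
| 1.00 | 94.0% | 89.1% |
| 0.95 | 95.0% | 90.9% |
| 0.88 | 96.3% | 93.1% |
| 0.77 | 98.0% | 96.1% |

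**The case against.** The strongest case against acting is that nothing is broken. Adjusting for the randomisation factor is valid and fits the design. No bias, type I error problem or contradiction arises, and the stated power reproduces. All of that stands.

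The second objection concerns the quality of the covariate, and it stands too. The outcome is treated bleeds from an electronic diary under a 72-hour rule, excluding procedural bleeds (SAP 2.3.1.2). The history is a plain number of bleeds; for the intra-patient comparison, Protocol 3.3.3 takes it "from the medical record and/or Study BH29768". Protocol 3.3 says that routine reporting "is not standardized and can be incomplete in routine clinical care". SAP 2.3.2.5 limits intra-patient comparisons to participants of the non-interventional study because only there is the detail comparable, and SAP 4.5.2.6 notes that few such patients were randomised to Arm A or B. Most prior counts in those arms therefore come from outside that study. The simulation has no reporting error, so its gains are on the favourable side for a given ρ. This does not favour one arm, since the count precedes randomisation. The two-class factor also depends on how well prior bleeds were reported.

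A reader might infer a fixed gain, such as 11–23% at no cost. If prior and on-study counts share a single gamma frailty (pre-selection variance 0.5, 0.8 or 1.2), the reduction is indeed 11%, 16% or 23%. But that model makes history carry over fully and has no reporting error. In Step 3, reductions of that size need ρ of roughly 0.7 to 0.9, and the documents support no particular value. Nor is the cost zero. A functional form must be fixed in advance, and one more parameter is estimated with 17 controls, in a plan that falls back on the Van Elteren test if NB convergence is questionable (SAP 4.5.1).

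A reader might also extend the gain to every bleed endpoint. It was examined for one bleed rate only; a total historical count may predict joint or spontaneous bleeds less well.

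**Conclusion.** The point holds as an efficiency suggestion. The primary model discards within-class information that the trial already collects, and recovering it takes one covariate. The size is uncertain: from 1–2% variance inflation if the count is not prognostic, through about 5% reduction at a correlation of 0.5, to over 20% at 0.9. These figures rest on the assumed lognormal prior rates, the plan's own rates and variances, and error-free prior counts.

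The trade is favourable because the possible loss is small and bounded, while the gain is useful if history predicts on-study bleeding even moderately. It does not support a claim that the planned analysis is wrong or the trial underpowered against its stated target. The per-comparison target of more than 90% is met without the change.

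**What to change.** In SAP 4.5.1, keep the <9/≥9 stratification factor and add log(number of bleeds in the 24 weeks before study entry) as a continuous covariate in the NB model. Entry requires at least 5 bleeds, so the log is defined for every eligible randomised patient. Carry the change by reference into SAP 4.5.2.1–4.5.2.3. State that it does not extend to the intra-patient comparisons in 4.5.2.4 and 4.5.2.6, which borrow the primary model but use pre-study bleeding as the comparator. Name the factor-only model as a sensitivity analysis in 4.5.4. Align Protocol 6.5.1 or record the difference.

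The cost is one extra parameter, a log-linear form to be fixed before the data are analysed, and up to 1–2% variance inflation if the count carries no information. No new data, visits or patients are needed. The choice must be pre-specified, because adding the covariate after seeing results would not be credible.
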